Currently, standard constraints for liver SBRT planning stipulate that 700 cc of “uninvolved liver”, i.e., the volume of liver minus the gross tumor volume (GTV), should receive <15 Gy. This constraint is derived from a phase I study conducted at the University of Colorado (which itself was based on surgical data showing that 75-80% of the liver can be safely resected).[9, 17] Since 25% of the assumed average liver volume of 2000 cc is 500 cc, 700 cc was used as a conservative limit. The basis for 15 Gy was that its BED is 40 Gy₃ which is less than the whole liver tolerance of 49.5 Gy₃ as determined from an early RTOG dose escalation study of whole liver RT.[18] The current constraint does not take into account the functional residual capacity of the untreated liver. However, information about regional variations in liver function could help to evaluate the safety of RT in patients who are borderline candidates for liver RT based on their liver function. In this protocol, we will meet the standard physical constraints but plan to increase safety further by attempting to decrease dose to functional areas.

The indocyanine green (ICG) retention study is presently the gold standard for assessing liver function, but this study only provides information about global liver function.[19] An ICG retention at 15 minutes (ICG15) of less than 14% has historically been used as a cutoff to select patients for major hepatectomy, but subsequent trials have shown that well-selected patients with ICG15 values above this cutoff had similar outcomes as those with lower ICG15 values[20, 21] According to the 2016 NCCN hepatobiliary guidelines, ICG15 is widely used in Asia but not in Western countries. Two studies from the University of Michigan reported baseline ICG values in patients’ pre-treatment. They reported ICG clearance as ICG half-life, whereas the surgical data looks at ICG retention at 15 minutes (ICG15). In a total of 29 patients, the values ranged from 3.75 minutes to 14.5 minutes, which would correlate with an expected ICG15 of 6.25% to 48.8%. In this study, 14 of 29 (48.3%) of patients would have had a ICG value >14%. Clearly, the patients undergoing radiation therapy for liver tumors can have a large variation in their liver function. Having more data as to what functional residual capacity correlates with the ability to safely deliver radiation therapy would be beneficial.

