4.4 Primary Endpoint

1. The functional reserve of liver will be calculated for both a plan that takes the HIDA scan into account and a plan that does not take this into account. The functional reserve will be calculated by (number of counts outside 15 Gy isodose line / total number of counts within the liver) * global liver function.

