4.6 Exploratory Endpoints

1. Correlations between radiation dose to the normal liver and the risk of RILD.
2. Correlation between the quantitative data from fMRI and HIDA scan values. Also, a preliminary exploration of the doses at which changes in fMRI are seen.
3. The rate at which the HIDA changed enough such that the radiation plan could have been adapted to decrease the amount of functional liver receiving >15 Gy.

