13.4 Sample Size

20 subjects will be enrolled with the goal of 15 evaluable subjects who have one month follow-up information available. Although Child-Turcotte-Pugh A and Child-Turcotte-Pugh B7 patients are both included, they will not be analyzed separately.

The next possible step would be a Phase I trial that incorporates the data from HIDA- and functional MRI-guided radiation planning in order to permit dose escalation in liver SBRT as well as the treatment of patients with poor liver function, who are not currently SBRT candidates. As the technique of functionally guided radiation has not been previously used in the treatment of liver

tumors, a 5% relative improvement in functional reserve of the liver will be considered as beneficial. If the use of HIDA scans shows beneficial functional reserve of the liver in at least 3 of 15 of the subjects, this will help encourage further study on the use of HIDA scans for planning. If the true rate of HIDA in improving functional reserve by 5% is at least 30% or higher, we will have 87% probability detecting it with this rule:

True probability HIDA is better than conventional plan by 5%	.1	.2	.25	.3	.4	.5
Probability of seeing at least 3 where HIDA is better	0.18	0.60	0.76	0.87	0.97	≥ 0.99

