13.8 Analysis of Exploratory Objectives

To assess the correlation between the radiation dose and the risk of RILD, graphs and descriptive statistics will be used to see if any relationships may exist.

Spearman's correlations will be used to compare output from each of the HIDA and fMRI scans to see if any measures correlate to each other.

To assess significant change in HIDA and fMRI scans, the plan based off the HIDA scan done at mid-therapy would be re-optimized, retrospectively. The proportion of patients who have a change in the regional distribution of function after the initial radiation treatments will be determined. If this re-optimized plan reduces the functional liver exposed to <15 Gy by 5% or more, this would be considered significant and will provide a potential idea about the feasibility of potential adaptive radiotherapy.

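### Section 13.8 applies the 5% cut-off to functional liver below 15 Gy, while the endpoint in 4.6 concerns functional liver above 15 Gy; the sign is probably a typing error.

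*Combined protocol and SAP*

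**What the plan says.** Section 4.6 defines the third exploratory endpoint as a rate: how often the HIDA scan had changed enough that the plan could have been "adapted to decrease the amount of functional liver receiving >15 Gy". It does not say how large the decrease must be.

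Section 13.8 gives the method and the threshold. On the method: "the plan based off the HIDA scan done at mid-therapy would be re-optimized, retrospectively". On the threshold: "If this re-optimized plan reduces the functional liver exposed to <15 Gy by 5% or more, this would be considered significant". The same sentence says the result will inform the feasibility of adaptive radiotherapy.

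Three other places show which side of 15 Gy the trial wants to enlarge:

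- Section 4.4 builds the primary endpoint, functional reserve, from "number of counts outside 15 Gy isodose line / total number of counts within the liver", scaled by global liver function. Function outside the 15 Gy line is what counts as reserve.
- Section 2.0 describes the standard constraint for 700 cc of uninvolved liver: "the volume of liver minus the gross tumor volume (GTV), should receive <15 Gy".
- Section 13.4 says "a 5% relative improvement in functional reserve of the liver will be considered as beneficial", so a larger share below 15 Gy is the benefit.

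**The concern.** The endpoint is a fall in functional liver above 15 Gy. The rule that scores it is a fall in functional liver below 15 Gy. Since 13.8 holds the only cut-off, the analyst has two poor options. Following the text literally would count the wrong subjects as showing a significant change. Silently reversing the sign would depart from the written plan.

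At stake is the reported proportion of subjects for whom mid-course adaptation looked worthwhile, which the protocol intends as early evidence on adaptive radiotherapy. Nothing confirmatory depends on it.

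**Working it through.** **The plan's own figures.** Section 13.8 states no computed figure. The only probabilities in the statistical section are in the 13.4 table, for at least 3 of 15 subjects. The exact binomial tail gives 0.184, 0.602, 0.764, 0.873, 0.973 and 0.996 for true rates 0.1, 0.2, 0.25, 0.3, 0.4 and 0.5. The table has 0.18, 0.60, 0.76, 0.87, 0.97 and ≥ 0.99, so it reproduces. This point does not depend on it.

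**Direction on one scan.** Let T be total functional counts in the liver, L the part below 15 Gy and H the part at or above it, so L + H = T. With both plans scored on one scan, T is fixed.

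- Rule as written, 5% relative: L′ ≤ 0.95 L. Then H′ = T − L′ ≥ H + 0.05 L, which exceeds H.
- A better-sparing plan has H′ < H, hence L′ > L, and cannot meet the rule.
- If 5% means five percentage points of T, a fall of 5 points in L is a rise of 5 points in H.

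The reversal therefore does not depend on the starting split or on how the 5% is read.

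**Size over a range of starting splits.** The documents do not give the share of function below 15 Gy, so 50% to 90% is an assumption. The 5% is taken as relative.

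| L at start | H at start | As written: H after (relative change) | With >15 Gy: L after (relative change) |
|---|---|---|---|
| 50% | 50% | 52.5% (+5.0%) | 52.5% (+5.0%) |
| 60% | 40% | 43.0% (+7.5%) | 62.0% (+3.3%) |
| 70% | 30% | 33.5% (+11.7%) | 71.5% (+2.1%) |
| 80% | 20% | 24.0% (+20%) | 81.0% (+1.25%) |
| 90% | 10% | 14.5% (+45%) | 90.5% (+0.56%) |

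**Illustration with the documents' volumes.** Section 2.0 supplies both inputs: "Since 25% of the assumed average liver volume of 2000 cc is 500 cc, 700 cc was used as a conservative limit". Assume uniform function, ignore the GTV and use one scan. The part below 15 Gy is 700 cc, and the part above is 2000 − 700 = 1300 cc.

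- As written: 0.95 × 700 = 665 cc below; 2000 − 665 = 1335 cc above; 35/1300 = +2.7% above. This worse plan is called significant.
- With >15 Gy: 0.95 × 1300 = 1235 cc above; 2000 − 1235 = 765 cc below; 65/700 = +9.3% below. This better plan fails the rule as written.

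**The case against.** The strongest reply is that this is an obvious slip with little practical effect. Section 4.6 is unambiguous, Sections 2.0, 4.4 and 13.4 agree with it, and the reference to adaptive radiotherapy makes sense only if re-optimization improves sparing. An analyst is unlikely to report worse plans as a benefit. That is fair and is why the point is minor. It does not remove the conflict, because no other text corrects the only cut-off.

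The reversal also depends on scoring both plans on one scan, and 13.8 does not say which scan scores the original plan. If raw counts from two scans with different totals were compared, both parts could fall. For an assumed total going from 100 to 80 and a share below 15 Gy going from 70% to 75%, L goes from 70 to 60 (−14.3%) and H from 30 to 20 (−33.3%). This stands as a limit on the claim of reversal. The mismatch with 4.6 remains either way.

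The 700/2000 cc example is not a typical plan: 700 cc is a minimum for uninvolved liver, and uniform function sets aside the trial's premise of regional variation. That is also fair; the example shows direction only.

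Finally, the direction could be restored by keeping <15 Gy and changing the verb to an increase, which would match the reserve measure in 4.4 and 13.4. The two repairs set different thresholds. At an assumed 70/30 split, a 5% relative cut above 15 Gy is a 2.1% gain in reserve, whereas a 5% relative gain below 15 Gy is an 11.7% cut above it (3.5/30). Section 13.8 exists to analyse the endpoint in 4.6, and that endpoint is worded in terms of liver above 15 Gy, so the sign change is the closer repair.

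**Conclusion.** The concern holds, at minor severity. The dose side in 13.8 contradicts the endpoint it is meant to score. With both plans on one scan, the written rule is met only by plans that expose more functional liver to 15 Gy or above, whatever the starting split. That it is a typing error is an inference, though a well-supported one. No number of misclassified subjects is claimed, since the documents give no data from which to estimate one. The analysis is exploratory, retrospective and descriptive, and no treatment decision depends on it.

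**What to change.** In 13.8, change <15 Gy to >15 Gy so that the criterion matches 4.6, after checking the sign against the source file. The cost is one character, with no new data and no change to treatment.

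An optional clause in the same sentence would settle what the sign change leaves open:

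- whether the 5% is a relative reduction;
- which measure it applies to: HIDA counts as in 4.4, or a named contour from 9.4;
- whether both plans are scored on the mid-treatment HIDA scan.

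The authors should note that a 5% relative cut above 15 Gy equals the 5% relative gain in reserve of 13.4 only when function is split 50/50, and confirm which of the two they intend.

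### The adaptive-planning threshold in section 13.8 runs in the wrong direction as printed, and its 5% has no stated denominator to make it comparable with the 5% in section 13.4

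*Combined protocol and SAP*

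**What the plan says.** Section 4.4 defines functional reserve as the share of liver counts lying outside the 15 Gy isodose line, multiplied by global liver function. Section 13.4 sets the size of benefit for the comparison of HIDA-guided with conventional planning: "a 5% relative improvement in functional reserve of the liver will be considered as beneficial". The quantity and the scale are both explicit there: spared function, relative change.

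The adaptive endpoint appears in two places. Section 4.6(3) asks how often the HIDA scan changed enough that "the radiation plan could have been adapted to decrease the amount of functional liver receiving >15 Gy". It gives no percentage. Section 13.8 supplies one: "If this re-optimized plan reduces the functional liver exposed to <15 Gy by 5% or more, this would be considered significant". It does not say whether the 5% is relative or in percentage points, or what it is a percentage of.

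**The concern.** Sections 4.6(3) and 13.8 describe the same endpoint with opposite inequalities. An analyst who follows section 13.8 to the letter would count as significant those re-optimized plans that spare less functional liver.

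The obvious repair, changing below to above 15 Gy, fixes the direction but leaves a second gap. The 5% then applies to irradiated function, while the 5% in section 13.4 applies to spared function. The two are complements, so the same percentage means different amounts of liver. A reader who sees one 5% rule for HIDA planning and another for adaptive planning will assume that they are equally demanding, and they generally are not. Section 13.8 uses its rule to comment on the feasibility of adaptive radiotherapy, so the rule should be one that the protocol would recognise elsewhere as a benefit.

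**Working it through.** **Inputs.** The reserve formula is in section 4.4, the 5% relative gain in section 13.4, the direction of the adaptive aim in section 4.6(3), and the unlabelled 5% in section 13.8. Let f be the share of liver counts outside 15 Gy under the comparator plan and G the global liver function, so reserve R = f × G and irradiated function is (1 − f) × G. With both plans scored on one scan, G cancels from relative changes. The documents give no value of f, so the values below are assumptions.

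**The plan's own figures.** Section 13.4 works with benefit "If the use of HIDA scans shows beneficial functional reserve of the liver in at least 3 of 15 of the subjects" and states that "we will have 87% probability detecting it with this rule". The exact binomial probability of at least 3 of 15 at true rates 0.1, 0.2, 0.25, 0.3, 0.4 and 0.5 is 0.184, 0.602, 0.764, 0.873, 0.973 and 0.996. The printed table reproduces, and nothing in this point alters it.

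**Section 13.8 as printed.** Function below 15 Gy is f × G, which is the reserve itself. A 5% relative reduction takes R to 0.95R, a 5% loss of reserve.

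**Section 13.8 repaired to above 15 Gy.**
- Relative reading: irradiated share falls from (1 − f) to 0.95(1 − f), so f rises by 0.05(1 − f). Relative reserve gain = 0.05(1 − f)/f.
- Percentage-point reading: f rises by 0.05. Relative reserve gain = 0.05/f.
- Conversely, the section 13.4 gain (f to 1.05f) needs a relative cut in irradiated function of 0.05f/(1 − f).

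| f | Reserve gain, 5% relative cut | Reserve gain, 5-point cut | Cut in irradiated function needed for a 5% reserve gain |
|---|---|---|---|
| 0.35 | 9.3% | 14.3% | 2.7% |
| 0.5 | 5.0% | 10.0% | 5.0% |
| 0.6 | 3.3% | 8.3% | 7.5% |
| 0.7 | 2.1% | 7.1% | 11.7% |
| 0.8 | 1.25% | 6.25% | 20% |
| 0.9 | 0.56% | 5.6% | 45% |

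On the relative reading the adaptive rule is laxer by a factor f/(1 − f): 1.5 at f = 0.6, 4 at 0.8 and 9 at 0.9. It equals the section 13.4 rule at 0.5 and is stricter below that. On the percentage-point reading it is stricter for every f below 1.

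**What range of f is open.** The low value comes from the planning limit in section 2.0 ("assumed average liver volume of 2000 cc is 500 cc, 700 cc was used as a conservative limit"): 700/2000 = 0.35 if function is uniform. That is a limit, not a typical plan. For the other side, take one 6 cm spherical lesion (the maximum in section 5.2), the section 9.4 PTV margins, uniform function and a 2000 cc liver, and assume that the 15 Gy line lies a further 1 to 2 cm out. The irradiated ellipsoid is then (4/3)π × 4.5² × 5 = 424 cc to (4/3)π × 5.5² × 6 = 760 cc, so f is about 0.79 to 0.62. Smaller lesions raise f. Smaller livers, several lesions or wider dose spread lower it.

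**Ceiling.** Since f cannot exceed 1, a 5% relative gain in reserve is impossible when f is above 1/1.05 = 0.952.

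**The case against.** The strongest reply is that the mismatch of scale is not in the printed text. As printed, section 13.8 refers to spared function, the same quantity as in section 13.4, and the only plain error is direction. Changing the verb from reducing to increasing, instead of changing the inequality, would put the rule on the spared-function side, and with a relative 5% it would match section 13.4 exactly. This is correct. The scale problem depends on which repair is chosen and on a relative or absolute choice that section 13.8 leaves open. But section 4.6(3) is worded in terms of liver above 15 Gy, so reversing the inequality is the repair that the protocol itself suggests, and it is the one that creates the mismatch.

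A reader might go further and infer that the adaptive rule is met by far smaller gains than the section 13.4 rule, so that adaptive re-planning would look significant more often. The documents do not support that. It needs the relative reading and f well above 0.5, and neither is stated. How often a threshold is met also depends on the gains that can be achieved. The two comparisons differ (HIDA against conventional planning, and re-optimization on a mid-treatment scan), and no distribution of gains is given for either.

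It can also be said that two different questions need not share a threshold, that the endpoint is exploratory with no pass mark, and that no comparison of the two rates is planned. All three are true, and they limit the consequence. They do not excuse a rule that, followed literally, scores harm as success.

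**Conclusion.** Wrong as written. Section 13.8 contradicts section 4.6(3) on direction, and that needs no assumption. Once it is read with section 4.6(3), its 5% is on irradiated function with no denominator and is not comparable with the 5% relative reserve gain of section 13.4. The implied reserve gain on the relative reading runs from 9.3% at f = 0.35 to 0.56% at f = 0.9. At f = 0.8 alone, the unstated choice between relative and percentage points moves it from 1.25% to 6.25%. Which rule is stricter cannot be settled from the documents, because f is not given.

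The reach is narrow: one exploratory endpoint in a pilot study. The 3-of-15 rule and its probability table stand. The ceiling at f = 0.952 is arithmetic, and a reader might take it as a flaw in the primary rule, but nothing in the documents shows that any subject will be near it. It is worth reporting and is not a ground for changing that rule.

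**What to change.** In sections 4.6(3) and 13.8, define the endpoint by the section 4.4 formula. Score the original and the re-optimized plan on the same mid-treatment HIDA scan, so that global function cancels and a change in function between scans does not enter the comparison. Call the change significant if functional reserve rises by at least 5% relative, as in section 13.4. This settles direction, quantity and denominator together.

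Also report, for each subject, f under the comparator plan and the relative change in irradiated function, and note any subject with f above 0.952, for whom a 5% relative gain cannot occur.

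The cost is wording and a little analysis on dose and count maps that the study already needs. The adaptive rate may move in either direction compared with a rule on irradiated function.

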13.9 Interim Analysis

No interim analysis will be performed for this study.

14.0 DATA FORMS AND SUBMISSION SCHEDULE

This study will utilize electronic Case Report Form completion in the OnCore® database. A calendar of events and required forms are available in OnCore®. The OnCore® database is a comprehensive, web-based, Clinical Trial Management System (CTMS) which utilizes an Oracle database. OnCore® was developed by Forte Research Systems, Inc. and is used by the IUSCC Clinical Trials Office (CTO) and supported by the Indiana Clinical and Translational Sciences Institute (CTSI). OnCore® properly used is compliant with Title 21 CFR Part 11.

OnCore® provides users secure access with unique IDs/passwords and restricts access by assigned roles, from any location, to record, manage, and report on data associated with the operation and conduct of clinical trials.

All source documents are to remain in the subject's clinic file. All documents should be kept according to applicable federal guidelines. Clinical trial data in OnCore® are periodically monitored by the IU Simon Cancer Center Data Safety Monitoring Committee.

15.0 SUBJECT CONSENT AND PEER JUDGMENT

The protocol and informed consent form for this study must be approved in writing by the appropriate Institutional Review Board (IRB) prior to any subject being registered on this study.

Changes to the protocol, as well as a change of principal investigator, must also be approved by the Board. Records of the Institutional Review Board review and approval of all documents pertaining to this study must be kept on file by the investigator (housed in the Clinical Trials Office) and are subject to inspection at any time during the study. Periodic status reports must be submitted to the Institutional Review Board at least yearly, as well as notification of completion of the study and a final report within 3 months of study completion or termination.

The study will be conducted in compliance with ICH guidelines and with all applicable federal (including 21 CFR parts 56 & 50), state or local laws.

16.0 DATA AND SAFETY MONITORING PLAN

Investigators will conduct continuous review of data and patient safety. **Monthly review meetings** for moderate risk trials are required and will include the principal investigator, clinical research specialist and/or research nurse (other members per principal investigator's discretion). **Monthly** meeting summaries should include review of data, the number of patients, significant toxicities as

described in the protocol, and responses observed. Summaries will be submitted and reviewed monthly by the DSMC. Submit to [contact].

Study Auditing and Monitoring

All trials conducted at the IUSCC are subject to auditing and/or monitoring. Reports will be reviewed by the full DSMC at the time of study review (Reference Risk Table in full DSMC Charter).

Early Study Closure

At any time during the conduct of the trial, if it is the opinion of the investigators that the risks (or benefits) to the patient warrant early closure of the study, this recommendation should be made in writing to the Data Safety Monitoring Committee. Alternatively, the DSMC may initiate suspension or early closure of the study based on its review of the investigator reports.

Reporting Guidelines

The DSMC has streamlined the reporting process by utilizing reports from OnCore[®]. This has allowed direct view of reports within the Clinical Trials Management System (CTMS); thus discontinuing paper reports. SAE reports are entered into OnCore[®] monthly and reviewed by the DSMC chair and/or coordinator monthly. Findings will be reported to the full DSMC at the time of study review.

Reporting Death

Death will be reported per local IRB reporting guidelines (Section 5.8 of the Unanticipated Problems and Noncompliance SOP).

Study Accrual Oversight

Accrual data will be entered into the IU Simon Cancer Center OnCore[®] system. The Protocol Progress Committee (PPC) reviews study accrual twice per year while the PPC coordinator reviews accrual quarterly.

Protocol Deviations

Protocol deviations are entered into OnCore[®] and reviewed by the DSMC chair and/or coordinator monthly. Findings will be reported to the full DSMC at the time of study review.

